10. ADVERSE EVENT REPORTING

10.1. Definitions

An Adverse Event (AE) is any untoward medical occurrence in a study participant regardless of its relationship to study treatment. A treatment-emergent AE is an adverse event occurring during the period between the first dose and 30 days after the final dose of the study medication. A Serious Adverse Event (SAE) is any untoward medical occurrence that results in death, is life-threatening, requires hospitalization or prolongation of an existing hospitalization, results in persistent or significant disability, or is a congenital anomaly/birth defect. Important medical events that do not fall into the above categories may also be considered an SAE when, based on medical judgment, such events may jeopardize the patient's safety and require medical/surgical intervention to prevent one of the outcomes listed in the SAE definition. The term SAE is not intended as a measure of severity or intensity. All AE's/SAE's that occur after the time of informed consent will be reported.

A Suspected Adverse Reaction is any adverse event for which there is a reasonable possibility that the drug caused the adverse event. For the purposes of IND safety reporting, "reasonable possibility" means there is evidence to suggest a causal relationship between the drug and the adverse event. Suspected adverse reaction implies a lesser degree of certainty about causality than adverse reaction, which means any adverse event caused by a drug. An Unexpected Adverse Event or Unexpected Suspected Adverse Reaction is an adverse event or suspected adverse reaction that is not listed in the investigator brochure or is not listed at the specificity or severity that has been observed; or, if an investigator brochure is not required or available, is not consistent with the risk information described in the general investigational plan or elsewhere in the current application, as amended. For example, under this definition, hepatic necrosis would be unexpected (by virtue of greater severity) if the investigator brochure referred only to elevated hepatic enzymes or hepatitis. Similarly, cerebral thromboembolism and cerebral vasculitis would be unexpected (by virtue of greater specificity) if the investigator brochure listed only cerebral vascular accidents. "Unexpected", as used in this definition, also refers to adverse events or suspected adverse reactions that are mentioned in the investigator brochure as occurring with a class of drugs or as anticipated from the pharmacological properties of the drug, but are not specifically mentioned as occurring with the particular drug under investigation. An Expected Adverse Event or Expected Adverse Reaction is any adverse experience that has been identified in nature or severity in the current investigator brochure and/or protocol.

10.2. Adverse Events Reporting

All AEs will be reported on the Adverse Events form that will be completed by the study staff, who are masked as to study treatment assignment, at each regular follow-up visits. This will insure that AEs are ascertained in an unbiased manner using the same standardized methodology for participants in both treatment arms. Forms will include standardized questions relating to specific events of import in diabetic patients on either of the study treatment arms as well as any significantly abnormal physical finding identified on examination and any significantly abnormal laboratory results obtained on the patient between visits or at the time of the visit. AEs reported or ascertained between clinic visits will be captured and reported at the time of the next schedule visit. Pre-existing conditions (that is, any condition that was known to be present prior to the signing of informed consent or was identified during the screening procedures at Visit 1) will not be considered or recorded as AEs unless the condition worsens in intensity or frequency after Visit 1. Likewise, continuing AEs will not be reported as AEs at subsequent visits unless they increase in severity or frequency between visits, they results in criteria for a SAEs, and/or they resolve between visits. Each site will be responsible for reporting all AE's to their IRB according to its AE reporting policy and procedures.

10.3. Assessment of Causality and Severity

The seriousness of adverse events will be ascertained by the study staff according to the criteria listed in 10.1 and the need for further evaluation, follow-up, or referral. The relationship between study participation and AEs will be determined according to the following criteria:

A. Not related – temporal relationship of the onset of the event, relative to study participation, is not reasonable or another cause can by itself explain the occurrence of the event.

B. Possibly related – temporal relationship of the onset of the event, relative to study participation, is reasonable but the event could have been due to another, equally likely cause.

C. Probably related – temporal relationship of the onset of the event, relative to study participation, is reasonable and the event is more likely explained by the study treatment than by another cause.

D. Definitely related – temporal relationship of the onset of the event, relative to study participation, is reasonable and there is no other cause to explain the event.

10.4. Serious Adverse Events Reporting

See Section 15 – Data and Safety Monitoring Plan.

11. STATISTICAL ANALYSIS

This section presents a summary of the planned statistical analyses. A statistical analysis plan (SAP) will be written for the study that contains detailed descriptions of the analyses to be performed. The SAP will be written prior to database lock.

11.1. Analysis Population

For most of the analyses, including the primary efficacy analysis described in section 11.3, an intention to treat (ITT) analytical approach will be employed. Accordingly, the population for statistical analysis will consist of all randomized study participants considered in their original randomization group, regardless of treatment discontinuation or loss to follow-up.

Selected secondary efficacy analyses will be performed using a per-protocol analytical approach. In this case, the analysis population will consist of the ITT population excluding data points which 1. had cumulative exposure to the study medication from randomization that was less than 80% of the theoretical full exposure; or 2. during major protocol deviations (e.g., treatment with prohibited medications), which could affect primary outcome.

11.2. Initial Data Analysis

The initial data analysis will be performed to detect any differences in distributions of characteristics measured at baseline, 4, 20, 36, and 38 months (0, 16, 80, 156, and 164 weeks, respectively) between study groups. The number of patients screened, enrolled, and completing the study will be summarized within and across study centers. Measures of central tendency (means, medians) and variability (standard deviations, ranges) will be estimated from the data for continuous variables. Frequency distributions will be provided for categorical data. This preliminary analysis step will provide us with insight into data, distributions of the variables considered, and will allow us to find additional invalid values not detected earlier during data validation.

11.3. Primary Efficacy Analysis

For the primary endpoint (iGFR at the end of the 2-month wash-out period following the 3-year intervention), we will follow the recommendations by Carpenter et al^{38,39} and perform the analysis by means of a linear model for correlated errors with general/unstructured covariance matrix using all available iGFR measures (including those at baseline, 80, 156, and 164 weeks, respectively) as the dependent variable. By conditioning on the baseline iGFR measure we will also effectively use this variable as a covariate. Treatment group, study center, stratifying variables, albuminuria status (subjects who qualified by ACR or AER or were albuminuric at baseline vs. subjects who did not qualify by eGFR slope and were normoalbuminuric at baseline), baseline AER, time, and time by treatment interaction will also be included as covariates in the model. Three features make this analytical approach especially attractive:

1. If there is no dropout (a very unlikely case), the estimate of the treatment effect at the end of the 2-month wash-out period following the 3-year intervention and its precision obtained using this approach will be exactly the same as those based on a classical approach employing an analysis of covariance (ANCOVA) model with treatment group, study center, iGFR and AER/ACR measured at baseline included as covariates.
2. If the iGFR measure at the end of the wash-out period is missing, we will be able to efficiently use the information contained in the intermediate iGFR measurements obtained at 80 and 156 weeks, by virtue of them being correlated with the GFR measurement at washout. Estimate of the treatment effect obtained this way is valid under the missing at random (MAR) assumption. This is in contrast to the ANCOVA approach, which would lead to the loss of this information and would require a more stringent assumption about the mechanism of data missingness, i.e. a missing completely at random (MCAR) mechanism.
3. The underlying analytical framework allows the use of all post-randomization data and is well suited to investigate the reason for withdrawal, for example to study whether participants having low iGFR values are more likely to withdraw.

Calculations will be performed using SAS PROC/MIXED. Results of the analysis will be expressed in terms of point estimate and its corresponding 95% confidence interval for the treatment effect at the end of the 2-month wash-out period following the 3-year treatment and will be accompanied by the corresponding p value.

11.4. Secondary Efficacy Analyses

1. The effect of treatment on the iGFR at the end of the 3-year treatment period (before the washout) will be evaluated using the same analytical approach employed for the primary outcome.
2. The effect of treatment on the eGFR at 4 months after randomization will be evaluated using the same analytical approach employed for the primary outcome.
3. The iGFR and eGFR time trajectories, estimated from periodical iGFR measures and quarterly serum creatinine and cystatin C measurements using the CKD-EPI SCr and the CKD-EPI SCr-SCysC equations^{34,35}, respectively, will be analyzed using linear mixed-effects models.⁴⁰⁻⁴² The main objective of the analysis will be to construct confidence interval for the effect of the intervention over three years of observation (treatment main effect) and investigate whether the effect of the intervention changes with time (time by treatment interaction).
4. Time to serum creatinine doubling or ESRD in the two treatment groups is subject to censoring due to dropouts or reaching the end of study before the participant experiences the event. Survival time will be defined as the time from randomization to the event (the first of serum creatinine doubling from baseline or occurrence of ESRD, defined as eGFR \leq 15 ml/min/1.73 m², hemodialysis, or kidney transplant) or, for participants who did not experienced an event, to the last study visit. Data will be summarized by means of Kaplan-Meier survival curves and by providing the proportions of participants surviving without events at 1, 2, 3 years, and at the end of the wash-out period along with their 95% CIs. Given the potentially small number of events, differences between study groups will be tested by means of the log rang test or by means of simple Cox regression models including a limited number of predictors in addition to treatment group.
5. The effect of treatment on the AER at the end of the wash-out period, based on the geometric mean of two AER measured at this time point and adjusted for the geometric mean of AER at baseline (Visit 3 and 4), will be investigated in a linear regression model framework as in the case of the primary outcome.

6. The effect of treatment on the AER at the end of the treatment period, based on the geometric mean of the AER measures at visit 15 and 16 adjusted for the geometric mean of AER at baseline (Visit 3 and 4) will be investigated as in #5.
7. Time to fatal or non-fatal cardiovascular events will be analyzed as proposed for time to serum creatinine doubling or ESRD.
8. We will perform a per-protocol analysis (as defined in 11.1) for the primary efficacy endpoint (iGFR at the end of the 2-month wash-out period following the 3-year intervention).

11.5. Incomplete Data

Missing values represent a potential source of bias. Efforts will be made to keep all participants in the study. If this is not feasible, at least some information regarding the status at the end of the trial will be obtained. For randomized patients, the number of completers and dropouts will be summarized. This procedure will help to compare characteristics of the participants' groups who drop out from the study with those who completed the study by treatment group, within and across study centers. The models considered in the proposal allow for a missing at random (MAR) mechanism. MAR means that the missing values mechanism can be explained by observed data and does not depend on the *unobserved* values of outcome measures. The differences in distributions between characteristics of the groups may indicate potential sources of bias due to missing values. For instance, some patients may dropout from the study due to *unobserved* factors related to the intervention itself. If we suspect such bias is present, the methods discussed in this section, assuming (MAR), are not applicable. We will incorporate plausible missing values mechanism into the model as discussed in Little⁴³ and investigate how such mechanism may affect the estimates of treatment effect. To this end, sensitivity analyses will be conducted involving selection and/or pattern-mixture models⁴⁴ with an appropriate submodel used to describe dropout.

11.6. Pilot participants

All pilot participants who were already randomized to allopurinol or placebo during the pilot will be included in the final analysis of the pivotal trial. Those who do not consent to the pivotal trial will be treated as having dropped from the study at a time corresponding to their last pilot visit. Sensitivity analyses will be performed to investigate whether results may be potentially affected by the roll-over of pilot subjects in the pivotal trial.

11.7. Model assumptions and alternative analyses

Model assumptions will be thoroughly checked for individual and systematic departures, using informal, e.g. inspection of residuals, and formal methods such as score test for extra parameter or methods based on likelihood displacement. If individual outliers are detected, their influence will be evaluated using influence diagnostics methods based on comparing estimates from models fitted to data with and without outlying values. Whenever we are not successful in fitting the parametric model (linear or non-linear), then non-parametric analyses and/or transformation of the variables involved in the analysis will be considered. To investigate the potential hemodynamic influence of allopurinol on treatment effect, in addition to the aforementioned analyses, we will consider models including the post-randomization measure of GFR at 4 months as an additional covariate. To investigate the possible presence of heterogeneity in the response to allopurinol, subgroup analyses (based on the primary efficacy analysis described in section 11.3, with the inclusion of an interaction term of the treatment group by the subgroup variable) will be performed by age groups (≤ 40 and > 40 yrs), gender, racial/ethnic group, HbA1c (≤ 7.8 and $> 7.8\%$), serum uric acid (≤ 6.0 and > 6.0 mg/dl), baseline iGFR (≤ 70 ml/min and > 70 ml/min/1.73m²), AER at baseline (≤ 300 and > 300 mg/24 hr), and albuminuria status (subjects who qualified by ACR or AER or were albuminuric at baseline vs. subjects who did not qualify by eGFR slope and were normoalbuminuric at baseline). To investigate possible influence of using selected covariates on the treatment effect estimate in the models considered in Section 11, we will

perform appropriate sensitivity analyses. These additional analyses will be considered as strictly exploratory.

11.8. Safety Analyses

Adverse events will be independently reviewed by an independent data safety monitoring board (DSMB, see Sections 15 and 16). All safety data will be available in data listing in the clinical protocol report. Data will be described in terms of descriptive statistics and presented by treatment group. Presentation will include graphs (scatterplots, boxplots, histograms), measures of central tendency (mean, median) and variability (confidence intervals) for continuous variables and frequency tables for categorical variables.

11.9. Interim Analysis

No formal interim analyses of efficacy to stop for benefit or futility are planned, given the timing of the primary endpoint.

11.10. Sample Size

Since a variance-covariance matrix for the iGFR measures is not available and this matrix is essential in order to perform formal power calculations for a model with correlated errors, we performed alternative power calculations based on an intent-to-treat analysis within an ANCOVA framework. Specifically, we assumed that the primary hypothesis is tested in the following model:

$$M1: \text{iGFR at washout} = \text{iGFR at baseline} + \text{treatment group}$$

Compared to the model that will be used in the primary analysis, model M1 is simplified in two aspects. First, it does not use information from iGFR values measured at intermediate time points. Second, it does not include covariates such as the stratifying variables (HbA1c and UA) or other GFR predictors such as baseline AER. Both of these aspects may lead to loss of precision of the treatment effect estimate. Consequently, our sample size calculations should be considered as conservative.

The hypothesis being tested, i.e. the effect of treatment on iGFR at washout, corresponds to testing whether the treatment group factor in Model M1 is significant. The choice of the ANCOVA model for the purpose of power calculations is sensible, as residuals from a univariate model involving baseline iGFR as covariate fitted to data from RASS study conform to normal distribution. Sample size calculations were performed based on Cohen⁴⁵ and making the following assumptions:

1. Postulated effect on iGFR at washout (\cdot) = 3 ml/min/1.73 m². We deem this effect to be clinically meaningful and attainable. It is clinically meaningful because it would translate on average into a 10-year delay in the progression to ESRD. It is attainable because it is smaller than the difference in 3-year GFR that we observed in the JKS between subjects with serum UA \geq 4.5 mg/dl compared to those with levels below this value. The postulated effect was based on the following changes in GFR levels in the two treatment groups:
 - a. Untreated group = 3 ml/min/1.73 m² per year. This estimate is based on data from the Joslin Kidney Study (JKS), in which the median GFR loss among 43 subjects meeting the above criteria was 3.1 ml/min/1.73 m² per year, with 70% of subjects having a GFR loss $>$ 1.5 ml/min/1.73 m² per year. Also, among 116 subjects from Steno who met the albuminuria and GFR criteria, but for whom serum uric acid values were not available, the median GFR loss was 3.3 ml/min/1.73 m² per year, with 71% of subjects having a GFR loss $>$ 1.5 ml/min/1.73 m² per year.
 - b. Treated group = 2 ml/min/1.73 m² per year. The average GFR loss in the JKS subjects with serum UA $<$ 4.5 mg/dl was 1.5 ml/min per year. On this basis, we conservatively assumed that the allopurinol treatment, if effective, would decrease the GFR loss to 2 ml/min per year (a 33% decrease compared to the untreated group).

2. Standard deviation (SD) of residual error = 10.1 ml/min/1.73 m². This was estimated based on the root-mean-squared error from a regression model with eGFR at 3 yrs as the dependent variable and baseline eGFR as the independent variable fitted to data concerning T1D patients from the Joslin Kidney Study meeting the PERL inclusion criteria.

Assuming a two-sided alpha error equal to 0.05, the effective sample size needed to detect the pre-specified treatment effect ($\delta = 3$ ml/min/1.73 m²) at washout adjusted for baseline iGFR with 80% power is equal to n=180 per group. To take into account the anticipated overall dropout rate (up to 5%/yr or 15% over the entire duration of the study) and drug discontinuation or non-compliance in the treatment group (up to 2%/yr or 6% over the entire duration of the study), and to maintain the desired

power of at least 80%, it will be necessary to recruit n=240 subjects per group. In Table 1, we show the power of the proposed sample size for Model M1 under different dropout and non-compliance scenarios. We also provide the corresponding power for a model (Model M2) including the two stratifying variables (Hb1Ac and UA) and baseline AER as covariates to illustrate the effect of adding these variables to Model M1. In this analysis, we assumed that adding these covariates reduces the residual variance by 10%, which corresponds to these covariates explaining merely 4% of the total iGFR variation over and above the variability explained by iGFR at baseline. As shown in Table 1, once these covariates are accounted for, power is expected to exceed the conservative estimates provided by Model M1 and reach almost 90% for 15% dropout and 6% non-compliance rates.

Table 1. Power to detect treatment effect for two ANCOVA models under different drop-out and non-compliance scenarios.

Overall Dropout (%)	Non-compliance (%)	Model	
		M1	M2
9	0	.87	.92
12	0	.86	.91
15	0	.85	.90
9	6	.83	.89
12	6	.82	.88
15	6	.80	.87

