6.7.2. iGFR time trajectory estimated from repeated iGFR measurements	19
6.7.3. eGFR at 4 months after randomization (Visit 7).....	20
6.7.4. eGFR time trajectory	20
6.7.5. Time to serum creatinine doubling or ESRD	21
6.7.6. Urinary AER at the end of the wash-out period.....	21
6.7.7. Urinary AER during the last three months of the treatment period (Visits 15 and 16).	22
6.7.8. Time to fatal or non-fatal cardiovascular events	22
6.8. Other analyses	23
6.8.1. Subgroup analyses.....	23
6.8.2. Analyses of safety outcomes	24
6.8.3 Analyses of other measures	24
6.8.4. Analysis of the effect of post-randomization sUA changes on iGFR value at Visit 17	25
6.8.5. Time to 40% eGFR decrease.....	26
6.8.6. Time to doubling of serum creatinine, end-stage renal disease (ESRD), or cardiovascular/renal death.....	26
6.9. Model assumptions and alternative analyses	27
ACKNOWLEDGEMENTS.....	28
REFERENCES	29
APPENDIX I. Study Objective, Study Design, Outcomes & Statistical Analysis and Data Management Sections from Protocol.....	30

1. Overview

DESIGN:

- Multicenter, double-blind, placebo-controlled, parallel-group randomized clinical trial.
- N=530 total number of subjects

STUDY POPULATION:

- Type 1 Diabetes
- Inclusion/Exclusion Criteria listed in the Study Protocol

STUDY TREATMENTS:

- Oral allopurinol or placebo administered for 3 years followed by a 2-month drug washout

PRIMARY OUTCOME MEASURE:

[figure not shown]
- iGFR at the end of the 2-month wash-out period following the 3-year intervention

STATISTICAL ANALYSIS PLAN:

- This plan will be finalized prior to the database lock and unblinding of treatment groups

2. Schema

Figure 2.1. PERL Study Schema

3. Rationale for Adjustments of Statistical Analysis Plan as Compared to Protocol (Version 10, approved by DSMB on March 6, 2018)

Changes from the protocol-specified definitions of aims, outcomes, and statistical analytical approaches are outlined below. These changes reflect internal discussions since the initiation of the study that have not been incorporated as protocol amendments, but were discussed during the preparation of the Statistical Analysis Plan. These changes and the rationale for their implementation are documented herein and represent changes made prior to the database lock and unblinding of the study.

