power of at least 80%, it will be necessary to recruit $n=240$ subjects per group. In Table 1, we show the power of the proposed sample size for Model M1 under different dropout and non-compliance scenarios. We also provide the corresponding power for a model (Model M2) including the two stratifying variables (Hb1Ac and UA) and baseline AER as covariates to illustrate the effect of adding these variables to Model M1. In this analysis, we assumed that adding these covariates reduces the residual variance by 10%, which corresponds to these covariates explaining merely 4% of the total iGFR variation over and above the variability explained by iGFR at baseline. As shown in Table 1, once these covariates are accounted for, power is expected to exceed the conservative estimates provided by Model M1 and reach almost 90% for 15% dropout and 6% non-compliance rates.

Table 1. Power to detect treatment effect for two ANCOVA models under different drop-out and non-compliance scenarios.

Overall Dropout (%)	Non-compliance (%)	Model	
		M1	M2
9	0	.87	.92
12	0	.86	.91
15	0	.85	.90
9	6	.83	.89
12	6	.82	.88
15	6	.80	.87

PERL

PREVENTING EARLY RENAL LOSS
IN DIABETES

**A multicenter clinical trial of allopurinol to prevent GFR loss in
type 1 diabetes**

**Statistical Analysis Plan
Prepared by PERL DCC**

February 22, 2017

Contents

1. Overview	4
2. Schema	5
3. Rationale for Adjustments of Statistical Analysis Plan as Compared to Protocol (Version 9, approved by DSMB on August 16 th , 2016)	6
3.1. Use of modified Intention-to-Treat (ITT) Analysis Population.....	6
3.2. Simplified model for the primary efficacy analysis	6
4. Study Aim.....	8
5. Study Endpoints and Other Outcomes	9
5.1. Primary Endpoint	9
5.2. Secondary Outcome Measures	9
5.2.1. Secondary endpoint: iGFR at the end of the 3-year treatment period (Visit 16, before the washout)	9
5.2.2. Secondary endpoint: iGFR time trajectory estimated from repeated iGFR measurements.....	9
5.2.3. Secondary endpoint: Estimated (eGFR) at 4 months after randomization (Visit 7).....	9
5.2.4. Secondary endpoint: Estimated GFR (eGFR) time trajectory.....	9
5.2.5. Secondary endpoint: Time to doubling of serum creatinine or end-stage renal disease (ESRD).....	9
5.2.6. Secondary endpoint: Urinary AER at the end of the two-month wash-out period (Visit 17)	10
5.2.7. Secondary endpoint: Urinary AER during the last three months of the treatment period (Visits 15 and 16).....	10

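### The Model M2 power column in Table 1 does not follow from the stated 10% variance reduction: the planning row gives .84, not .87 or almost 90%

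*Protocol*

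**What the plan says.** Protocol section 11.10 bases the sample size on Model M1, an ANCOVA of washout iGFR on baseline iGFR and treatment. The difference to be detected is 3 ml/min/1.73 m². The other inputs are "Standard deviation (SD) of residual error = 10.1 ml/min/1.73 m²" and "Assuming a two-sided alpha error equal to 0.05". The section arrives at 180 evaluable per group for 80% power, raised to 240 per group for up to 15% dropout and 6% non-compliance.

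Model M2 adds the two stratifying variables and baseline AER, "to illustrate the effect of adding these variables to Model M1". For M2 the protocol says "we assumed that adding these covariates reduces the residual variance by 10"%, which it equates to 4% of total iGFR variation. Table 1 gives power at 240 per group for both models under six combinations of dropout and non-compliance. In the last row (15% dropout, 6% non-compliance) it prints .80 for M1 and .87 for M2. The text describes that M2 result differently: "power is expected to exceed the conservative estimates provided by Model M1 and reach almost 90% for 15% dropout and 6% non-compliance rates".

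The current SAP repeats the sentence and the table in Appendix I, section 11.10 ("reach almost 90% for 15% dropout and 6% non-compliance rates"). Its Overview gives "N=530 total number of subjects", not 480.

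**The concern.** M1 and M2 are described as differing in one respect only, the residual variance. Once a method reproduces the M1 column, the M2 column should therefore follow from a single substitution. It does not, and every M2 entry is too high. The sentence under discussion then goes further than the table it cites.

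What is at stake is the credibility of the claimed gain from covariate adjustment. Section 11.10 calls the M1 calculation conservative partly because it leaves these covariates out, and the M2 column is the only figure that shows by how much. As printed, a reader cannot tell which variance reduction was used, and the text credits the covariates with more power than the stated assumption yields.

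**Working it through.** **Inputs, all from protocol section 11.10:** two-sided alpha .05; effect 3; residual SD 10.1 for M1; residual variance 10% lower for M2; 240 recruited per group; dropout 9, 12 or 15%; non-compliance 0 or 6%.

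**Method.** The protocol names a power textbook but does not say how dropout and non-compliance enter. I took:

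- n per group = 240 × (1 − dropout), giving 218.4, 211.2 and 204;
- effect = 3 × (1 − non-compliance), giving 3 or 2.82;
- noncentrality = effect / (SD × √(2/n)), with df = 2n − 3 (two groups and one covariate);
- power from the noncentral t.

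**Step 1: the plan's own figures.** At 180 per group with effect 3 and SD 10.1, power is .802, which agrees with the stated 180 for 80%. The M1 column below matches Table 1 to two decimals in every row, so this handling of dropout and non-compliance is well supported.

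**Step 2: change only the variance.** The M2 SD is 10.1 × √0.9 = 9.58.

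| Dropout | Non-compliance | M1 printed | M1 computed | M2 printed | M2 computed | M2 excess (points) |
|---|---|---|---|---|---|---|
| 9% | 0% | .87 | .872 | .92 | .904 | 1.6 |
| 12% | 0% | .86 | .861 | .91 | .894 | 1.6 |
| 15% | 0% | .85 | .849 | .90 | .884 | 1.6 |
| 9% | 6% | .83 | .829 | .89 | .866 | 2.4 |
| 12% | 6% | .82 | .817 | .88 | .855 | 2.5 |
| 15% | 6% | .80 | .803 | .87 | .843 | 2.7 |

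Worked for the last row: n = 240 × 0.85 = 204 and effect = 3 × 0.94 = 2.82.

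- M1: noncentrality = 2.82 / (10.1 × √(2/204)) = 2.82; power .803.
- M2: noncentrality = 2.82 / (9.58 × √(2/204)) = 2.97; power .843.

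The gain from the covariates in this row is 4 points (.803 to .843), not the 7 that the table shows (.80 to .87).

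**Step 3: does another reading recover the column?**

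- *Normal approximation:* M2 is .905, .896, .885, .868, .856, .844. The excess is still 1.4–1.5 points at 0% non-compliance and 2.2–2.6 at 6%.
- *Rounding n up to whole patients:* no M2 value moves by more than .0013.
- *10% off the SD rather than the variance:* .931, .923, .914, .899, .889, .878, above every printed value.
- *Removing non-compliers from n, or halving the dilution:* the last M2 row becomes .862–.866, but the last M1 row becomes .824–.829 against a printed .80, so M1 no longer reproduces.
- *One-sided alpha:* M1 in the last row becomes .880, against .80.

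**Step 4: what reduction does the printed column need?** All six rounded M2 values are matched only by a variance reduction of about 15.65–16.3% (noncentral t) or 15.2–15.9% (normal). On the protocol's ratio of 10% residual to 4% total, 15–16% of residual variance is about 6% of total iGFR variation (0.4 × 15–16%). If almost 90% is read as .895, the last row would need a reduction of about 23%.

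**The case against.** The strongest reply concerns weight. M2 is offered as an illustration. The 240 per group rests on M1, which reproduces exactly, and neither M1 nor M2 is the model used for the primary analysis. Recomputed M2 power still exceeds M1 in every row and stays above 80%. At the SAP's N=530 (265 per arm assumed) with the same 10% reduction, 15% dropout and 6% non-compliance, power is .876, so the printed .87 is reached at the enrolled size. All of this stands, and it limits the point to a minor one.

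A second reply is that the method is inferred and that the second decimal depends on it: row 2 is .89 by noncentral t and .90 by the normal approximation, and row 5 is .85 or .86. That is fair for those two rows. The noncentral t is preferred because the normal approximation gives .805 where the last M1 entry is .80, which is a narrow basis for the choice. Under either method the last M2 row is .84.

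Third, the three rows without non-compliance miss by less than 2 points, and almost 90% is loose prose beside a table that shows .87. Both are true. The rows nevertheless all err in the same direction by more than rounding allows, and the prose overstates both the table and the recomputed value. The 23% figure depends on reading almost 90% as .895, a threshold the protocol does not set, and the conclusion does not need it.

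**Conclusion.** The concern holds, as a minor internal error. Under the protocol's stated 10% reduction in residual variance, M2 power at 240 per group is .90, .89, .88, .87, .85, .84. The printed column is too high by 1.6 points in the rows with 0% non-compliance and by 2.4, 2.5 and 2.7 points in the rows with 6%. The sentence in the text overstates the planning row further.

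This rests on dropout reducing n and non-compliance diluting the effect proportionally. The documents do not spell that out, but it reproduces the whole M1 column. The documents do not show whether the 10%, the column or a calculation input is at fault. The M1 column, the 240 per group and the planned analysis are unaffected.

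**What to change.** Reconcile the stated reduction with the table in one of two ways:

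1. Keep the 10% assumption. Restate the M2 column as .90, .89, .88, .87, .85, .84 (noncentral t throughout) and change the sentence to about 84% for 15% dropout and 6% non-compliance.
2. Keep the printed column. State and justify the variance reduction of about 15–16% that it requires (about 6% of total iGFR variation) and change the sentence to 87%.

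In either case, name the power method under the table and say how dropout and non-compliance enter. The cost is a text and table edit in protocol section 11.10 and in its copy in SAP Appendix I. Sample size, design and analysis do not change.
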